4.9.2 Duration of Response

Duration of response will be defined for patients with CR or PR only as the interval between the date of initial documentation of a response and the date of the first documented evidence of progressive disease based on independent radiographic assessment or death, whichever occurs first. Clinical progression at EOT/EOS without radiographic assessment could be considered as an event in a sensitivity analysis. Patients who have the event after the start of subsequent anticancer therapy/procedure, or are progression-free and alive at the time of clinical cut-off, or have unknown status, will be censored at the last valid tumor assessment on or before the start of subsequent anticancer therapy/procedure or clinical cut-off time. When a subsequent anticancer therapy is used and progressive disease (based on radiographic or clinical progression at EOT/EOS) is observed within 6 days, they will be considered as the same visit (within the protocol specified +/-6 days visit window) and the patient will be counted as having an event (losing the response).

Patients with no post-baseline disease assessment will be censored on Day 1.

Duration of response will be estimated and displayed for the all-treated population using Kaplan-Meier methods (SAS[®] PROC LIFETEST). A Kaplan-Meier plot will be presented.

A sensitivity analysis of DOR will be conducted in which the DOR for patients undergo SCT will not be censored at SCT.

A sensitivity analysis of DOR per investigator assessments will also be conducted.

Subgroup analysis may be provided for disease subtype, disease stage, double/triple hit (yes/no), bulky disease (yes/no), GCB/ABC, transformed (yes/no), age group, response to the first line and/or most recent line of prior systematic therapy (relapse: CR+PR vs. refractory: SD+PD vs. other: NE + missing), best response to loncastuximab tesirine (CR/PR), and other relevant variables.

4.9.3 Time to Response:

Time to response (TTR) is defined among patients who achieve either CR or PR as BOR before the start of subsequent anticancer therapy or procedure as the time from the first dose to the initial documented response. For this subset of patients, TTR will be summarized using descriptive statistics.

4.9.4 Complete Response Rate

Complete Response Rate (CRR) will be defined as the proportion of patients with a best overall response of CR. The percentage of CRR with its 95% CI will be presented.

4.9.5 Relapse-free Survival

Relapse-free survival will be defined among CR patients as the time from the date of the first complete response until the date of the first disease relapse based on independent radiographic assessment (i.e., disease progression for CR patients) or death, whichever occurs first. The date of disease progression will be defined as the earliest date of disease progression based on central review. Clinical progression at EOT/EOS without radiographic assessment could be considered as an event in a sensitivity analysis. For patients who have the event after the start of subsequent anticancer therapy/procedure, or are progression-free and alive at the time of clinical cut-off, or have unknown status, censoring will be performed using the date of the last valid disease assessment on or before the start of subsequent anticancer therapy/procedure or clinical cut-off time. When a subsequent anticancer therapy is used and progressive disease (based on radiographic or clinical progression at EOT/EOS) is observed within 6 days, they will be considered as the same visit (within the protocol specified +/-6 days visit window) and the patient will be counted as having an event (losing the response).

Patients with no post-baseline disease assessment will be censored on Day 1.

RFS will be estimated and displayed for the all-treated population using Kaplan-Meier methods (SAS[®] PROC LIFETEST). A Kaplan-Meier plot will be presented.

A sensitivity analysis of RFS will be conducted in which RFS for patients undergo SCT will not be censored at SCT.

A sensitivity analysis of RPS per investigator assessments will also be conducted.

4.9.6 Progression-free Survival

Progression-free survival is defined as the interval between the date of the first dose and the date of the first disease progression based on independent radiographic assessment or death, whichever occurs first. Clinical progression at EOT/EOS without radiographic assessment could be considered as an event in a sensitivity analysis. Patients who have the event after the start of subsequent anticancer therapy/procedure, or who are progression-free and alive at the time of clinical cut-off, or have unknown status, will be censored at the time of their last valid disease assessment on or before the start of subsequent anticancer therapy/procedure or

clinical cut-off. When a subsequent anticancer therapy was used and progressive disease (based on radiographic or clinical progression at EOT/EOS) were observed within 6 days, they will be considered as the same visit (within the protocol specified +/-6 days window) and the patient will be counted as having an event.

Patients with no post-baseline disease assessment will be censored on Day 1.

PFS will be estimated and displayed for the all-treated population using Kaplan-Meier methods (SAS[®] PROC LIFETEST). A Kaplan-Meier plot will be presented.

A sensitivity analysis of PFS will be conducted in which the PFS for patients undergo SCT will not be censored at SCT.

A sensitivity analysis of PFS per investigator assessments will also be conducted.

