8.1 Efficacy Assessments

Disease assessments will occur as per schedule of events (SoE) ([Table 1](#)) until progression. Disease assessments should take place at the timepoints specified even if study drug dosing is delayed. Additional disease assessments may be obtained, if clinically indicated.

Imaging and clinical examination for lymphoma will be performed at all disease assessment timepoints. All patients will have positron emission tomography - computed tomography (PET-CT) of the neck/chest/abdomen/pelvis and other areas of known or suspected disease performed at baseline. Patients with PET-avid disease at baseline should have PET-CT for all subsequent disease assessments. If disease is not PET-avid at baseline, computed tomography (CT) or magnetic resonance imaging (MRI) may be used for subsequent disease assessments. Patients whose disease is not PET-avid should have a bone marrow biopsy as part of their baseline staging and disease assessment if clinically appropriate.

Screening (Baseline) imaging must be performed within 4 weeks prior to C1D1.

During the treatment period, imaging will be performed 6 weeks and 12 weeks after C1D1, then every 9 weeks until EOT. Week 6 imaging should be performed within 5 days prior to C3D1 and Week 12 imaging should be performed within 5 days prior to C5D1. All other imaging should be performed within ± 2 weeks of the scheduled time point.

During the follow-up period, patients who discontinued study drug for reasons other than disease progression or initiation of other anti-cancer therapy except stem cell transplant, will have imaging performed every 12 (± 2) weeks until 1 year from EOT, then every 6 months until disease progression, up to 3 years from EOT.

Response data will be collected for patients who receive CAR-T therapy until 90 days after receiving CAR-T therapy.

If a scan has been performed within 8 weeks of EOT, it does not need to be repeated at EOT.

In case of dose delays, disease assessment should be maintained at the frequencies defined above.

The patient's response to treatment will be determined according to the 2014 Lugano Classification Criteria ([Appendix 2](#)) as CR, PR, stable disease (SD), or progressive disease (PD). Images will be obtained according to local site imaging protocols and will be submitted for central review. Submission instructions for central review will be provided in a separate manual.

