9.6.5 Progression-Free Survival

PFS will be defined among all treated patients as the time from first dose of study drug until the first date of either disease progression or death due to any cause. The date of disease progression will be defined as the earliest date of disease progression based on central review. For patients whose disease has not progressed at the time of the analysis, censoring will be performed using the date of the last valid disease assessment. The data will be analyzed by the Kaplan-Meier method. The median PFS time and 95% CI will be presented. Further details will be outlined in the SAP.

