3.3 Modifications to the statistical section of the protocol

NA.

4 Statistical methods

All analyses use SAS[®] version 9.4 or higher. All available data will be used in the analyses, and important data will be included in data listings, sorted by patient, and by visit within patient. Missing data will not be imputed, except via censoring in survival analyses and as otherwise specified.

Unless otherwise noted, categorical data will be presented using counts and percentages, with the number of patients in the analysis population as the denominator for percentages. Percentages will be rounded to one decimal place, except 100% will be displayed without any decimal places and percentages will not be displayed for zero counts. Continuous data, unless otherwise noted, will be summarized using the number of observations (n), mean, standard deviation (std), median, minimum, and maximum. Minima and maxima will be rounded to the precision of the original value, and means, medians, and 95% confidence intervals (CIs) if presented will be rounded to 1 decimal place greater than the precision of the original value. The std will be rounded to 2 decimal places greater than the precision of the original value, up to a maximum of 3 decimal places.

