4.9.1 Overall Response Rate

Overall response rate is defined as the proportion of patients who achieve either CR or PR as best overall response (BOR) as determined by central review according to the 2014 Lugano Classification criteria before the start of subsequent anticancer therapy or procedure. For the primary ORR analysis in the all-treated population, patients with a CR or PR will be counted as successes and all other patients (including those with missing response information) will be counted as failures.

The order of overall response category is: CR, PR, SD, NE, PD (including disease recurrence/ relapse). The overall response category will be derived based on response assessment performed on or before the start of subsequent anticancer therapy/procedure. Patients without documented subsequent anticancer therapy and/or with missing start date of anticancer therapy will be considered as not having received subsequent anticancer therapy. A BOR of SD can only be made after the patient is on-study for a minimum of 35 days after the first dose of study drug. Any tumor assessment indicating SD before this time period will be considered as NE for BOR if no assessment after this time period is available.

The overall response rate and the corresponding 95% two-sided exact confidence interval will be presented. Subgroup analysis may be provided for disease subtype, disease stage, double/triple hit (yes/no), bulky disease (yes/no), GCB/ABC, transformed (yes/no), age group, sex, country, response to the first line and/or most recent line of prior systematic therapy (relapse: CR+PR vs. refractory: SD+PD vs. other: NE + missing), and other relevant variables.

Percent change from baseline in the sum of product of the perpendicular diameters (SPD) for target lesions will be presented for available data in the all-treated population. These data will also be displayed as a waterfall plot, with vertical bars representing the sorted values of best percent reduction for each patient.

A sensitivity analysis of ORR determined by the independent reviewer's evaluation will be conducted for the per-protocol population if relevant.

A sensitivity analysis of ORR will be conducted in which best overall response is determined by investigators.

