4.9.7 Overall Survival

Overall survival is defined as the interval between the date of the first dose and the date of death from any cause. Patients who are known to be alive as of their last known status will be censored at their date of last contact. Patients who are lost to follow-up will be censored at the date the patient is last known to have been alive. The last confirmed alive date is the latest of the following: study visit date, telephone contact date, end of study last confirmed alive date, follow-up systemic (anticancer) therapy end date or start date (if ongoing or end date is missing), local or central radiologist scan date, or other date in the clinical database.

OS will be estimated and displayed for the all-treated population using Kaplan-Meier methods (SAS[®] PROC LIFETEST). A Kaplan-Meier plot will be presented.

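### SAP 4.9.6 counts death as a PFS event but, read literally, censors patients who die before any post-baseline scan on Day 1, which overstates PFS

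*SAP*

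**What the plan says.** SAP 4.9.6 runs PFS from first dose to the "date of the first disease progression based on independent radiographic assessment or death, whichever occurs first". Protocol 9.6.5 agrees: in all treated patients, PFS runs "until the first date of either disease progression or death due to any cause".

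The general censoring rule in SAP 4.9.6 covers three groups: patients whose event follows the start of subsequent anticancer therapy, "or who are progression-free and alive at the time of clinical cut-off, or have unknown status, will be censored" at the last valid disease assessment. A separate paragraph then states: "Patients with no post-baseline disease assessment will be censored on Day 1". It names no exception for death and no order of precedence.

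Protocol 8.1 sets the scan schedule: "During the treatment period, imaging will be performed 6 weeks and 12 weeks after C1D1, then every 9 weeks until EOT". SAP 3.3, headed "Modifications to the statistical section of the protocol", is answered as not applicable.

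**The concern.** Take a patient who dies in week 4, before any scan and without new therapy. The definition makes this an event in week 4, and the patient is in none of the three general censoring groups. The stand-alone sentence nevertheless censors the patient on Day 1, so the death leaves both the numerator and the risk set. Two programmers could follow the same text and report different curves.

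The literal reading errs in one direction only: it removes the earliest failures. In a single-arm trial no comparator carries the same error, so the absolute PFS estimate takes all of it. None of the listed PFS analyses (clinical progression as an event, transplant not censored, investigator assessment, per-protocol population, subgroups) lifts the Day 1 rule.

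**Working it through.** **Plan figures.** The documents state no PFS figure to reproduce. The design figure, power above 99% for ORR, does reproduce. With n = 140, a 20% null and 40% alternative, and one-sided 0.025, the exact test rejects at 39 or more responders (alpha 0.0158, power 0.9990). It does not depend on PFS.

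**Inputs from the documents.** N = 140; first post-baseline scan at week 6 (Protocol 8.1); historical median survival 6.1 months (Protocol 9.1).

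**Assumed inputs.** f, the share of treated patients who die unscanned and before new therapy; M, the median time to progression among the others, set at 3 and 5 months. Neither is in the documents.

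**Bound on f.** With a constant hazard, P(death before day 42) = 1 - 0.5^(42/(6.1 × 30.44)) = 14.5%, about 20 of 140. Longer median survival lowers it: 7.7% at 12 months and 3.9% at 24 months. The range shown below starts at 2% (about 3 of 140); at f = 0 there is no difference.

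**Effect on the curve.** After week 6, with deaths kept as events, S(t) = (1-f) × S_other(t), where S_other is the curve for the remaining patients. Under the literal rule the estimate is S_other(t). The ratio is 1/(1-f): 1.02 at 2%, 1.05 at 5%, 1.11 at 10% and 1.17 at 14.5%.

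**Closed form, exponential progression from first dose.** Overstatement of the median = -M × log2(1-f). Overstatement of six-month PFS = f × S_other(6), with S_other(6) = 0.5^(6/M), which is 0.25 for M = 3 and 0.435 for M = 5. Example, f = 5% and M = 5 months: 5 × 30.44 × 0.0740 = 11.3 days, and 0.05 × 0.435 = 2.2 points.

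**Simulation on the scan schedule.** 2,000 trials of 140 patients per setting. Progression is recorded at the next scan, early deaths are uniform on days 1 to 41, and administrative censoring is uniform on days 180 to 540.

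Each cell gives M = 3 / M = 5 months:

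| f | Median, closed form (days) | Median, simulated (days) | 6-month PFS, closed form (points) | 6-month PFS, simulated (points) |
|---|---|---|---|---|
| 2% | 2.7 / 4.4 | 3.7 / 4.4 | 0.5 / 0.9 | 0.7 / 1.0 |
| 5% | 6.8 / 11.3 | 11.3 / 12.0 | 1.3 / 2.2 | 1.6 / 2.6 |
| 10% | 13.9 / 23.1 | 25.4 / 24.4 | 2.5 / 4.4 | 3.3 / 5.2 |
| 14.5% | 20.6 / 34.4 | 34.8 / 34.8 | 3.6 / 6.3 | 4.7 / 7.4 |

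**A second model shape.** If progression cannot start until about week 6 and the observed median among scanned patients is 3 or 5 months, the shifts are smaller (400 simulated trials per setting, cut-off at 12 months). Deaths as events versus censored on Day 1:

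- f = 5%: median 2.90 vs 3.01 and 4.78 vs 5.02 months, a difference of 0.11 and 0.24 months (× 30.44 = 3 and 7 days). Six-month PFS 13.5% vs 14.2% and 39.4% vs 41.4%.
- f = 10%: median 2.78 vs 3.03 and 4.51 vs 5.07 months (8 and 17 days). Six-month PFS 12.8% vs 14.2% and 37.3% vs 41.4%.
- f = 15%: median 2.64 vs 3.01 and 4.21 vs 5.02 months (11 and 25 days). Six-month PFS 12.0% vs 14.1% and 35.2% vs 41.4%.

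The ratio of the six-month estimates matches 1/(1-f) in every case. The absolute shift depends on the assumed shape.

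**Other endpoints.** For ORR, "all other patients (including those with missing response information) will be counted as failures", so unscanned patients are already non-responders. SAP 4.9.7 has no Day 1 rule: "Overall survival is defined as the interval between the date of the first dose and the date of death from any cause". The same Day 1 sentence in SAP 4.9.2 and 4.9.5 applies to nobody, because a responder must have had a post-baseline assessment.

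**The case against.** The strongest reply is that the sentence is only a fallback date. The general rule censors at the last valid assessment; a patient without a post-baseline assessment has none to use, and the next paragraph supplies one. Its repetition under DOR and RFS, where it has no effect, looks like boilerplate. Protocol 9.6.5 counts death, and SAP 3.3 declares no change to the protocol's statistics, so the literal reading would be an undeclared change of endpoint. This is the more natural intent, and under it there is no bias. It is still an inference: the sentence covers every patient without an assessment, and nothing limits it to those already being censored. Protocol 9.6.5 does not settle the point fully either, because its censoring sentence speaks only of patients who have not progressed, whereas the DOR sentence in 9.6.2 also names death.

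The size is also open to challenge. The 14.5% bound applies historical survival to a population selected on performance status, organ function and non-bulky disease, and it treats every death before day 42 as unscanned. Protocol 8.1 allows additional assessments when clinically indicated, which would reduce f. These points stand, and 14.5% should be read only as an upper bound. For scale, a six-month PFS near 40% with 140 patients has a binomial 95% half-width of about 8 points (1.96 × sqrt(0.4 × 0.6/140)), more than any shift shown. That limits the practical effect but does not excuse a one-sided error.

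The deaths would still appear in OS, the death summaries and the patient listings. That makes the problem traceable but does not correct the PFS estimate.

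**Conclusion.** The concern holds: applied as written, the Day 1 sentence contradicts the event definition in the same section and biases PFS upward. What is established is a conflict in the text with a one-directional risk. Actual bias depends on how the rule is programmed and on whether unscanned early deaths occur.

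Under the literal reading, with M assumed at 3 to 5 months and across the models above, the overstatement is:

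- f = 5%: about 3 to 12 days in the median and 0.7 to 2.6 points at six months.
- f = 10%: about 8 to 25 days and 1.4 to 5.2 points.
- Upper bound, f = 14.5% to 15%: about 11 to 35 days and 2.1 to 7.4 points.

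Under the fallback reading, or if f = 0, the effect is zero. PFS is secondary and has no hypothesis test, so the primary conclusion, type I error and power do not change. It should be fixed before analysis; confidence is medium because the intended reading and f are unknown.

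**What to change.** Replace the sentence in SAP 4.9.6 with wording such as: *A patient who has no disease assessment after baseline and did not die before starting subsequent anticancer therapy is censored on Day 1. A death before the first post-baseline assessment and before any subsequent anticancer therapy is a PFS event on the date of death.* This keeps the SAP's censoring at new therapy and matches the event definition in both documents.

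Deleting the sentence from SAP 4.9.2 and 4.9.5 is optional tidying with no effect on results. If the protocol is amended for other reasons, the censoring sentence in 9.6.5 could name death as 9.6.2 does.

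The cost is one sentence and at most one line of programming. Reported PFS may be slightly less favourable than under the literal rule; nothing changes if a fallback date was always intended.

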4.9.7 Overall Survival

Overall survival is defined as the interval between the date of the first dose and the date of death from any cause. Patients who are known to be alive as of their last known status will be censored at their date of last contact. Patients who are lost to follow-up will be censored at the date the patient is last known to have been alive. The last confirmed alive date is the latest of the following: study visit date, telephone contact date, end of study last confirmed alive date, follow-up systemic (anticancer) therapy end date or start date (if ongoing or end date is missing), local or central radiologist scan date, or other date in the clinical database.

OS will be estimated and displayed for the all-treated population using Kaplan-Meier methods (SAS[®] PROC LIFETEST). A Kaplan-Meier plot will be presented.

4.9.8 Response for CAR-T patients

Response data collected after CAR-T therapy will be summarized separately.

4.10 Health-Related Quality of Life (HRQoL) Questionnaires

Scoring of QoL data and methods for handling of missing items or missing assessments will be based on each questionnaire's scoring manual.

4.10.1 European Quality of life (EuroQol)-5 Dimensions-5 Levels (EQ-5D-5L)

EQ-5D-5L is designed as an international, standardized, generic instrument for describing and evaluating QoL. The EQ-5D-5L consists of two parts:

- The descriptive system: QoL is classified according to five dimensions: mobility, self care, usual activities, pain/discomfort, and anxiety/depression. Each dimension comprises five levels of perceived problems (e.g., none, slight, moderate, severe, extreme).
- The visual analog scale (VAS): patients are asked to indicate their health state today on a VAS with the endpoints labeled 'the best health you can imagine' (score 100) and 'the worst health you can imagine' (score 0). Patients are asked to mark an "X"

on the VAS to indicate their own health and then to report the score in a text box. If there is a discrepancy between where the patient has placed the X and the number he/she has written in the box, the number in the box is to be entered in the CRF together with a comment indicating the discrepancy.

Individual dimension responses will be summarized at each scheduled assessment with frequency counts and percentage of patients.

Descriptive statistics (mean, standard deviation, median and range) of actual values and changes from baseline will be presented at each scheduled assessment for the EQ-VAS.

A change of 7 points in VAS from the baseline is considered minimally important difference (MID) (Pickard et al., 2007). Patients will be classified as improved/deteriorated based on the established MID, i.e., if at least one of the post-baseline scores improves/deteriorates by the magnitude of the MID compared to baseline score. Proportion of patients with improvement/deterioration will be summarized.

Completion rate of EQ-5D-5L will be calculated as the number of patients who complete at least one question of EQ-5D-5L (e.g., either in descriptive system or VAS) divided by the number of patients treated at a visit. Summary of completion rate at each visit will be presented.

Summary analyses will include data up to the start of subsequent anticancer therapy/procedure.

A data listing for each individual dimension response, and the EQ-VAS will be presented for each patient at each visit.

